	 Patients with existing gastrostomy and jejunostomy enteral feeding tubes, placed ≥ 3 months, undergoing replacement of feeding tube inpatient or outpatient. Willing to adhere to placement of study stoma site accessory and ability to take oral temperature at specified times. Stated willingness to comply with all study procedures and availability for the duration of the study. Willing to adhere to removal of study stoma site accessory at mo. 6 Exclusion Criteria Patient requires general anesthesia in an OR for tube changes Current use of steroids (any dose) daily ≥ 3 months including, but not limited to: prednisone, prednisolone, methylprednisolone, cyclosporine Current use of Immunosuppressants including, but not limited to: azathioprine, mycophenolate. BMI ≥ 40 Non-English speaking patients. Pregnant Women. Known allergic reactions to components of the study stoma site accessory: Medical Grade Silicone as described in Technical Data Prospectus from Dow Corning Corporation. Treatment with another investigational drug or device within 6 months of screening/baseline. Uncontrolled illness, recent open abdominal surgery or social situations that in the opinion of the investigative team would limit compliance with study requirements, including, but not limited to: Ongoing or active infection Psychiatric illness Unable to self-report Not ambulatory and incapable of carrying out all self-care Unsuccessful study accessory placement at initial replacement procedure
Number of	The study will enroll until 10 patients have had successful study stoma
	site accessory placement and reached the 2 week research follow-up
Subjects	visit.
Number of Sites	1
Sample Size	The sample size is 10 subjects. No formal sample size calculations were
Justification	performed for pre-market safety and efficacy data.
Study Hypothesis	The study is a pilot trial to access feasibility and safety with the aim to improve patient quality of life using pre and post measures. Patient quality of life assessment will be collected at baseline and 6 months for comparison.

Duration of Study	Expected enrollment period is 12 months. Follow-up duration is 6 months from initial replacement procedure with follow-up research visit at week 2 and phone calls at weeks 4 and 6 and month 6 and research visits at months 3, 4 and 6. The study will conclude 6 months from the enrollment of the last subject.

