- **Biocompatibility:** Raw material has been tested by the manufacturer to USP Class VI biocompatibility standards including:
 - Cytotoxicity
 - Skin Sensitization
 - 7-Day Implantation (systemic toxicity)
- Sterilization: Liquid silicone rubbers are regularly used in implanted medical devices subject to ethylene oxide sterilization. ETO has been demonstrated to have no adverse effects on the material. [12] [13]

STUDY INTERVENTION ADMINISTRATION

The study stoma site accessory consists of two components made of silicone elastomers specifically designed for the fabrication of medical devices and device components. The study stoma site accessory is compatible with commercially available enteral nutrition feeding tubes ranging from 16F to 20F and is intended for use during EN feeding tube standard practice replacement procedures. A rigid introducer, also made of silicone elastomers is included with each study accessory retention bumper and plug. The accessory components are supplied by Proto Labs and intended for one-time use. All three components will follow the ETO sterilization process and will be packaged and labeled as individual kits for accountability.

[figure not shown]

Fig.4 Stoma site accessory retention bumper and plug shown with SOC feeding tube

Instructions for use:

It is recommended that the tube French size selected be similar in size to the tube being removed, unless otherwise indicated by the physician. For questions or information about the tube's Instructions for Use (IFU) and a list of complete complications, please refer to the specific manufacturer's Instructions for Use. The following steps (1 through 5) are generalizable and not specific to any single manufacturer's IFU:

- 1. Select the appropriate size tube, remove from the package and inspect for any visible defects.
- 2. Using the manufacturer's specific type syringe, inflate the balloon through the balloon port using the specified mL units of sterile or distilled water for a standard balloon.
- 3. Remove the syringe and verify balloon integrity by gently squeezing the balloon to check for leaks. Visually inspect the balloon to verify symmetry. Symmetry may be achieved by gently rolling the balloon between the fingers. Reinsert the syringe and remove all the water from the balloon.
- 4. Using the syringe, flush water through balloon port to verify patency.
- 5. Lubricate the distal end of the tube with water-soluble lubricant. Do not use mineral oil or petroleum jelly.

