 - o Curvature and ribs to prevent accessory component from migrating
 - Indented to retention bumper
- Retention accessory bumper
 - Cupped, to allow greater mobility of flexible tubing
- Introducer
 - A double tapered plastic rod to assist the stoma site accessory plug onto the feeding tube. One end will insert into the distal end of the feeding tube. The accessory plug will be put onto the opposite end of the introducer and slide toward feeding tube.

Duration of implant or exposure

The average life span of PEG tubes is reported to be three months with tube degradation being the primary reason for replacement.[5] The study stoma site accessory is anticipated to be compatible with this duration based on similar SOC flange and button accessories. Maximum duration is unknown but could be significantly longer. Many commercial insurers will cover up to four tube replacements per calendar or rolling year. For study purposes the maximum length of time during which data will be collected for tubing change, as ordered by the treating physician, will be 6 months from initial study accessory placement.

[figure not shown]

Fig7. The study stoma site accessory depicting prevention of stomach acid from leaking on the abdominal wall.

Labeling/Accessory Tracking

The study stoma site accessory components will be sterilized by Cleveland Clinic's OR Surgical Processing Department. One retention bumper and one introducer will share one package since they are identical respectively in size. The accessory plug component will be in a separate package, labeled by size compatibility, e.g., "16 Fr, 20 Fr". All components will be double wrapped, barcoded and assembled as kits. Kits will be delivered for accountability and storage at room temperature in the Internal Medicine Research Unit (IMRU) located on the Cleveland Clinic (CC) Main Campus study site. Kits will be secured in a locked cabinet, accessible only to study personnel. Study personnel will maintain and monitor usage on a Case Report Form. IMRU study personnel can readily provide the study stoma site accessory kits to any procedure area on the Main Campus at short notice.

Manufacturing Information

Dow Corning® QP1-250

Dow Corning Corporation

Technical Data

Product Description

Liquid Silicone Rubber materials for device and component fabrication in the healthcare industry

APPLICATIONS

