Dow Corning® QP1-2XX Liquid Silicone Rubbers (LSRs) are platinum-catalyzed, heat-cured materials designed for the fabrication of medical devices and device components and for short term applications.

DESCRIPTION

Dow Corning QP1-2XX LSRs are a series of two-part platinum-catalyzed silicone elastomers specifically designed for liquid injection molding. Each elastomer is supplied in a two-part kit (Part A and Part B), equal portions (by weight) of which must be thoroughly blended together prior to use. The elastomer is thermally cured via an addition-cure (platinum-catalyzed) reaction. When blended and cured as indicated, the resulting elastomer consists of cross-linked dimethyl and methyl-innyl siloxane copolymers and reinforcing silica.

The Dow Corning QP1-2XX LSRs are available in a range of nominal hardness from 30 to 70, Durometer-Shore A. The elastomers can be used without any post cure; although, if necessary, this may be employed to stabilize the final properties. Furthermore, the cured elastomers are heat stable up to 204°C (400°F), can be autoclaved, and exhibit high gas permeability compared with most thermoset elastomers and thermoplastics.

General			
Material Status	 Commercial: Active 		
Literature 1	 Technical Datasheet (Engli 	ish)	
Search for UL Yellow Card	Dow Corning CorporationDow Corning®		
Availability	Africa & Middle EastAsia Pacific	Europe Latin America	North America
Features	AutoclavableFast CureFast Molding Cycle	 Food Contact Acceptable Good Colorability Good Processability 	High Gas PermeabilityLow ViscosityNon-Blooming
Uses	 Medical/Healthcare Application 	ations	
Agency Ratings	 USP Class VI 		
Processing Method	 Injection Molding 		

Test Method
n3 ASTM D792
;
3
Test Method
ASTM D412
ASTM D412
ASTM D412
n ASTM D624
Test Method
ASTM D224
)

Notes

¹ These links provide you with access to supplier literature. We work hard to keep them up to date; however you may find the most current literature from the supplier.

² Typical properties: these are not to be construed as specifications

³ 10/s

⁴ Die B

1 of

Form No. TDS-297761-ei

(ዚ)

UL and the UL logo are trademarks of UL LLC © 2018. All Rights Reserved. UL Prospector | [contact] or [contact] | www.ulprospector.com.

Document Created: Tuesday, May 1, 2018 Added to Prospector: March 2016 Last Updated: 3/29/2016

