- 3. Abdominal Pictures will be taken using Haiku software on CC issued cellphones and uploaded securely to the patient electronic chart. Pictures can be sent by the patient in MyChart for virtual visits scheduled through MyChart. Virtual visit abdominal pictures and screen captures are optional if not feasible to obtain at any study time points. Pictures are optional for study participation.
- 4. Medications of interest are primarily antibiotics.
- 5. Intervention at the study site occurs within 30 days of Informed Consent.
- 6. Daily temperature log to be completed by patient on days 3 through 10 and reported at week 2 and at months 3 and 4. Temperatures are self-recorded for all virtual visits; collection of temperature log is not required. The patient will be asked to call their treating physician if the patient is reporting a temperature over 100.4°F.
- 7. General assessment of the abdomen with stoma site inspection occurs at baseline evaluation, week 2 and months 3, 4 and 6 research visits and early termination. The week 2 and months 3 and 4 research visit may be scheduled in person or virtually. When the exam is virtual, the patient will be asked to report body temperature and vitals and allow/provide a visual of the abdomen for assessment and pictures when applicable. Pictures are optional for study participation.
- 8. Additional labs, radiology or other medically necessary procedures at week 2, months 3, 4 and 6 or early study termination as determined by the attending physician are considered standard of care. Patients will be asked to contact the study coordinator within 48 hours of a qualifying event, e.g., removal of study stoma site accessory that occurs at an external medical facility leading to participant early study termination.
- 9. Study personnel will schedule a research visit for months 3, 4 and 6 Study visits week 2 and at months 3 and 4 can be conducted virtually or in person. The month 6 study visit will be conducted in person for purposes of accessory removal.
- 10. Patients will be asked to contact study personnel to schedule in-person study accessory removal when removal is voluntary.

Number of patients

Ten patients to be recruited at one site, the Cleveland Clinic Main Campus. Patients who are prematurely withdrawn prior to week 2 follow-up will be replaced until the total number of patients exceeding week 2 equals 10.

Study Duration

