Expected enrollment period is 6 months, follow-up duration is 6 months from initial replacement procedure with follow-up visit at week 2 +/- 3 days and phone calls at weeks 4, 6 and early termination and months 3, 4 and 6 study visits. The study will conclude at 6 months from the last enrolled patient.

Patients undergoing intervention, surgical or repeat EN feeding tube replacement, after the initial replacement procedure that compromises the study stoma site accessory integrity will no longer be followed but will be included in the analysis of the endpoints until the time of intervention.

Stoma site study accessory removal with standard of care enteral feeding tube replacement and patient QOLs will be completed at month 6. The Investigator also must provide follow-up medical care for all patients who are prematurely withdrawn from the study or, must refer them for appropriate ongoing care.

Patient Characteristics

Inclusion criteria

In order to be eligible to participate in this study, an individual must meet all of the following criteria:

- Male or female, aged ≥22 and ≤85 Note: Because the study accessory is designed for adult use
 participants <22 years of age are excluded but will be eligible for future trials, if applicable
- Ability to understand and the willingness to sign a written informed consent document
- Patients with existing gastrostomy and jejunostomy enteral feeding tubes, placed ≥ 3 months, undergoing replacement of feeding tube inpatient or outpatient
- Willing to adhere to placement of study stoma site accessory and ability to take oral temperature at specified times
- Stated willingness to comply with all study procedures and availability for the duration of the study
- Willing to adhere to removal of study stoma site accessory at month 6

Exclusion criteria

An individual who meets any of the following criteria will be excluded from participation in this study:

- Patient requires general anesthesia in an OR for tube changes
- Current use of steroids (any dose) daily ≥ 3 months including, but not limited to: prednisone, prednisolone, methylprednisolone, cyclosporine
- Current use of Immunosuppressants including, but not limited to: azathioprine, mycophenolate.
- BMI ≥ 40
- Non-English speaking patients
- Pregnant Women
- Known allergic reactions to components of the study stoma site accessory: Medical Grade Silicone as described in Appendix A: Technical Data Prospectus from Dow Corning Corporation

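### The protocol cites a three-month tube life but plans six months on the accessory; few of the 10 patients may reach month 6, and the analysis has no method for unequal follow-up

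*Combined protocol and SAP*

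**What the plan says.** **Duration.** Under Duration of implant or exposure the protocol states: "The average life span of PEG tubes is reported to be three months with tube degradation being the primary reason for replacement". It continues: "The study stoma site accessory is anticipated to be compatible with this duration". It then calls the maximum duration unknown and possibly significantly longer, and sets six months as the limit for collecting data on tubing changes. The data sheet under Manufacturing Information describes the silicone as "designed for the fabrication of medical devices and device components and for short term applications". The biocompatibility list under Product Information, which refers to the raw material, includes "7-Day Implantation (systemic toxicity". Against these stands an inclusion criterion: "Willing to adhere to removal of study stoma site accessory at month 6". The Synopsis and the month-6 visit under Follow-Up agree with that criterion.

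**Follow-up.** Under Study Duration, patients whose repeat intervention or tube replacement compromises the accessory "will no longer be followed but will be included in the analysis of the endpoints until the time of intervention". Table 3 says the same.

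**Numbers.** "The sample size is 10 subjects", with no formal calculation (Synopsis). Under Number of patients: "Patients who are prematurely withdrawn prior to week 2 follow-up will be replaced until the total number of patients exceeding week 2 equals 10". No replacement is planned after week 2.

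**Analysis.** Data Collection and Analysis gives frequencies, percentages, 95% confidence intervals and a lost-to-follow-up proportion. Hypothesis Testing says quality of life is compared between baseline and 6 months. Table 1 and the visit lists put PROMIS 10 at baseline, month 6 and early termination. The Synopsis (quality-of-life questionnaires generally) and Table 3 (PROMIS 10 by name) also list week 2.

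**The concern.** Two issues come from the same passages.

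The first is internal consistency. The only duration with which the accessory is expected to be compatible is about three months, and the plan is to leave it in for six. Nothing in the documents bridges the gap.

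The second is statistical. The accessory is threaded onto the tube before the tube is inserted (Instructions for use) and is intended for one-time use (Study Intervention Administration). A tube change will therefore usually take it out and end follow-up. If tubes last about as long as the protocol says, most patients leave before month 6. Adverse events and leakage up to 6 months would then be percentages of 10 patients, many observed for only part of that time. Events that would have occurred later on the accessory go unseen, so a percentage over a fixed denominator tends to understate 6-month risk. Patients who do reach month 6 are those whose tube and accessory lasted, and the quality-of-life comparison would lean on them.

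**Working it through.** **Plan's own figure.** The sample size of 10 has no power, precision or attrition calculation behind it, so there is nothing to reproduce. The plan states no expected number at month 6.

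**Inputs.** 10 patients past week 2 (Number of patients). Visits at day 14, day 84 (month 3) and day 180 (month 6) (Follow-Up). Average tube life of three months, taken as 91.3 days (Duration of implant or exposure). The shape of the tube-life distribution and the 6- and 12-month averages are assumptions. Every tube change is taken to end follow-up, as the fitting steps and one-time use suggest.

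**Formula.** Replacement secures 10 patients at week 2, so the relevant quantity is conditional: P(in place at day t, given day 14) = S(t)/S(14).

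- Exponential, mean m: exp(−(t − 14)/m). At day 180 with m = 91.3: exp(−166/91.3) = 0.162.
- Exponential, median 91.3 days: 0.5^(166/91.3) = 0.284.
- Weibull shape 2, mean 91.3: scale = 91.3/Γ(1.5) = 103.0; exp(−(180/103.0)² + (14/103.0)²) = 0.048.
- Weibull shape 3, mean 91.3: scale = 91.3/Γ(4/3) = 102.2; the result is 0.004.

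| Assumed tube life | Expected of 10 at day 84 | Expected of 10 at day 180 | P(at least 5 of 10 at day 180) |
|---|---|---|---|
| Exponential, mean 3 months | 4.6 | 1.6 | 1.4% |
| Exponential, median 3 months | 5.9 | 2.8 | 12% |
| Weibull shape 2, mean 3 months | 5.2 | 0.5 | 0.01% |
| Weibull shape 3, mean 3 months | 5.8 | 0.04 | about 0% |
| Exponential, mean 6 months | 6.8 | 4.0 | 37% |
| Weibull shape 2, mean 6 months | 8.5 | 4.7 | 54% |
| Exponential, mean 12 months | 8.3 | 6.4 | 89% |
| Weibull shape 2, mean 12 months | 9.6 | 8.3 | 99.7% |

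**Observed exposure.** For the exponential cases, expected on-accessory time between day 14 and day 180 is m × (1 − S(180)/S(14)). With a 3-month mean: 91.3 × (1 − 0.162) = 76.5 of 166 days, or 46%. With 6 months: 182.6 × (1 − 0.403) = 109 days, 66%. With 12 months: 365.2 × (1 − 0.635) = 133 days, 80%. A percentage over 10 patients, read as a 6-month risk, treats this share as 100%.

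**Precision.** With no events among n patients, the upper exact 95% limit is 1 − 0.025^(1/n): 31% for n = 10, 71% for n = 3 and 84% for n = 2. A clean result over 10 patients looks much more reassuring than the 2 or 3 who may be observed for the whole period allow.

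**The case against.** **Device argument.** A reader might infer that six months exceeds what the material allows. The documents do not support that. The data sheet gives no number of days for short-term use, and the wording can be read as adding that use to device fabrication in general. The 7-day item is a test length in a list that need not be complete, not a limit on use. Product Information also says liquid silicone rubbers are regularly used in implanted devices. The protocol itself says the duration could be much longer than three months, and it lists long-term risks as unknown. What stands is the absence of any stated support for months 3 to 6.

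**Number reaching month 6.** A reader might infer that at most one patient will get there. That ignores the guarantee of 10 patients at week 2, the reading of three months as a median, and longer tube life. The three-month figure is a general one for PEG tubes, and this trial also takes PEGJ and DPEJ tubes. The protocol ends follow-up only when a change compromises the accessory. That every change would do so is an inference from fitting and one-time use, though a likely one.

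**Quality of life.** It would be wrong to say that month 6 is the only scheduled PROMIS 10 after baseline apart from early termination. That is Table 1's position; Table 3 adds week 2. Even so, no PROMIS 10 is scheduled between week 2 and month 6.

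**Mitigation.** Repeat intervention is already in the primary endpoint, so many tube changes are observed outcomes. Patients stay in the analysis until re-intervention. Early-termination questionnaires are attempted. Leakage and adverse events are also collected at weeks 2, 4 and 6 and months 3 and 4, and procedural success is judged at week 2. The study is a descriptive pilot. All this stands and makes the loss partial. It does not supply a method for unequal follow-up or a rule for early-termination PROMIS 10.

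**Conclusion.** The point holds in limited form. The three-month passage and the six-month plan are not reconciled, and the sponsor must reconcile them; which duration is right is not a question for this review.

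With a three-month average or median tube life, about 0 to 3 of the 10 patients past week 2 would reach month 6 with the accessory in place. With an average of 6 to 12 months, about 4 to 8 would. These ranges rest on assumed distributions, assumed longer averages, and the inference that a tube change normally ends accessory use. In the three-month cases, the 6-month adverse-event and leakage percentages and the baseline-to-month-6 PROMIS 10 comparison would rest on little and selected data. The week-2 success endpoint is not affected. The changes are cheap and worth making before the analysis is fixed.

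**What to change.** 1. **Reconcile** the duration, data-sheet and biocompatibility passages with the six-month plan, and state the expected attrition after week 2.

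2. **Report by interval.** Give adverse events, leakage and repeat intervention for 0–3 and 3–6 months, with numbers at risk and events per patient-month. Treat an accessory-ending tube change as an outcome, not as uninformative censoring. Any Kaplan-Meier figure should be supplementary: few would be at risk at month 6, and the reason for a tube change may be related to the events studied.

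3. **Quality of life.** Add PROMIS 10 at the existing month-3 visit, where about 5 to 6 of 10 would still have the accessory in the three-month cases. Settle whether it is collected at week 2, where the Synopsis and Table 3 disagree with Table 1 and the visit lists. Report early-termination PROMIS 10 as the last on-accessory value, separately from month-6 values.

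**Cost.** Protocol wording, one additional 10-item form per patient, one extra table, and wider stated uncertainty at 6 months. Recording the accessory's condition at removal is optional.
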